6.7.3. Laboratory Evaluations

Data for the following hematology, biochemistry, and urinalysis analytes recorded in the eCRF are to be measured at the scheduled visits.

Hematology:	hemoglobin, hematocrit, red blood cell (RBC) count, mean corpuscular hemoglobin, mean corpuscular volume, mean corpuscular hemoglobin concentration, platelet count, white blood cell count including differential (to also include absolute neutrophil, lymphocyte and eosinophil counts)
Serum Chemistry:	albumin, total and direct bilirubin, total protein, calcium, alkaline phosphatase, alanine aminotransferase, aspartate aminotransferase, blood urea nitrogen, creatinine, glucose, sodium, potassium, chloride, bicarbonate, lactate dehydrogenase, uric acid, highly sensitive C-reactive protein
Urinalysis (dipstick):	pH, specific gravity, blood, glucose, protein, ketones

In accordance with the baseline value definition in Section 5.1.2, the absolute change from baseline will be derived for quantitative data as follows:

$$\text{Absolute change (unit)} = (\text{post-baseline value} - \text{baseline value})$$

All laboratory data will be reported in SI units. Categorization of abnormal laboratory results along with clinical significance will be collected in a spreadsheet outside of the EDC database and utilized for the below outlined analysis. The same data (abnormal values) collected within the EDC will not be used in any statistical analysis. All normal results will continue to be collected and presented from the EDC. All quantitative laboratory test values at each assessed visit will be compared with the relevant reference range in SI units and categorized as:

- Low: Below the lower limit of the reference range.
- Normal: Within the reference range (upper and lower limits included).
- High: Above the upper limit of the reference range.

For summaries which present worst value with respect to the reference range at the subject level, low and high are each chosen in preference to normal values. For parameters with values that are both low and high, subjects will be counted within each category for worst value summary tables.

Laboratory data will be summarized by descriptive summary statistics for continuous and categorical variables for the Safety population by treatment group as follows:

- Observed values and change from baseline for each Treatment Period at each assessed visit for each standard continuous laboratory parameter;
- Number and percentage of subjects with categorized shift (low, normal, and high) values relative to the reference range at baseline compared to each post-baseline at each visit for each Treatment Period
- Number and percentage of subjects with worst categorized (low, normal, and high) values relative to the reference range;

Listings of all clinical laboratory data including derived change from baseline will be provided for the Safety population. Within each listing, laboratory values outside the normal ranges flagged as either high or low will be provided for applicable laboratory assessments. Listings of pregnancy results will also be provided for the Safety population.

6.7.4. Vital Signs

The analyses described below will be conducted for the following vital signs assessments respectively:

- systolic blood pressure (mmHg);
- diastolic blood pressure (mmHg);
- pulse rate (bpm);
- body temperature (°C).

In accordance with the baseline value definition in Section 5.1.2, the absolute change from baseline will be derived as follows:

Absolute change (unit) = (post-baseline value – baseline value)

The following will be summarized by treatment group for the Safety population:

- Observed values and percentage change from baseline at each assessed visit for each standard vital sign parameter using summary statistics for continuous variables;

A listing of all vital signs data including derived percentage change from baseline will be provided for the Safety population.

6.7.5. Electrocardiograms

The following electrocardiogram (ECG) assessments will be taken during the study:

- An overall investigator assessment classified as normal, abnormal, not clinically significant / abnormal, clinically significant
- Heart rate (bpm);
- RR interval (msec);
- PR interval (msec);
- QRS interval (msec);
- QT interval (msec);
- QTcB interval (msec).

In accordance with the baseline value definition in Section 5.1.2, the absolute change from baseline will be derived as follows:

Absolute change (unit) = (post-baseline value – baseline value)

The ECG findings will be summarized by treatment group for the Safety population as follows:

- Observed values and percentage change from baseline at each assessed visit for each ECG parameter using summary statistics for continuous variables;
- The ECG overall assessment as reported by the investigator will be summarized at each assessed visit by providing number and percentage of subjects within each assessment category;

A listing of all ECG data will be provided for the Safety population.

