13.1.4 Safety and Tolerability Analyses

Safety analyses will be conducted using data from the safety population. Safety variables include TEAEs; discontinuations because of AEs, clinical laboratory values that are abnormal and considered clinically significant, vital signs, and physical examination results. No formal inferential analyses will be conducted for safety variables.

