2.3. Sample Size and Power

The sample size was not determined based on statistical assumptions. Evaluation of up to 8 subjects per treatment group (16 subjects total) was considered sufficient to allow evaluation of the study's objectives.

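### Bazett is the only heart-rate correction of QT in the ECG tables, so a heart-rate change can appear as, or mask, a QTc change; adding Fridericia from data already collected would show it (minor)

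*SAP*

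**What the plan says.** SAP 6.7.5 lists the ECG parameters as an overall investigator assessment, "Heart rate (bpm"), "RR interval (msec"), PR, QRS, "QT interval (msec") and "QTcB interval (msec"). The last carries the usual label for Bazett's correction; the section gives no formula. Neither document names another correction, whether Fridericia, population-based or individual.

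The section derives absolute change from baseline, but the summary it specifies by treatment group is "Observed values and percentage change from baseline at each assessed visit for each ECG parameter using summary statistics for continuous variables". The investigator's assessment is tabulated by category, and "A listing of all ECG data will be provided for the Safety population".

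The Protocol's statistics section has no ECG subsection. Its section 13.1.4 states that "No formal inferential analyses will be conducted for safety variables". On the number of subjects (up to 16), SAP 2.3 states that "The sample size was not determined based on statistical assumptions".

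**The concern.** Bazett divides QT by the square root of RR. If QT in these subjects varies less steeply with RR than that, the correction overshoots: QTcB rises when heart rate rises and falls when heart rate falls, with no change in repolarisation. A table whose only corrected QT is QTcB cannot separate this from a real effect.

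The error runs both ways. A heart-rate rise under treatment could look like prolongation, and a fall could conceal one. This is the first study of SB-121 in humans (Protocol 5.3), safety is the primary objective (Protocol 6.1) and there is no data safety monitoring board (Protocol 12). The ECG summary will therefore be read as safety evidence even though it is descriptive. QT and RR, the two inputs for a second correction, are already in the dataset.

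**Working it through.** The plan gives no figure to reproduce: no QTc threshold, effect size or error rate. The calculation below illustrates size only.

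**Inputs from the documents.** QT, RR and heart rate are collected, and QTcB is the only corrected value (SAP 6.7.5).

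**Inputs assumed.** QT is 400 ms at 60 bpm, QT = 400 × RR^b with b between 0.30 and 0.50, there is no drug effect on repolarisation, and heart rate moves from 70 to 80 bpm.

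**Formulas.** RR in seconds = 60/HR. QTcB = QT/RR^(1/2). QTcF = QT/RR^(1/3).

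**One case in full (b = 1/3).**
- At 70 bpm, RR = 60/70 = 0.857 s, QT = 400 × 0.857^(1/3) = 380.0 ms and QTcB = 380.0/√0.857 = 410.4 ms.
- At 80 bpm, RR = 60/80 = 0.750 s, QT = 400 × 0.750^(1/3) = 363.4 ms and QTcB = 363.4/√0.750 = 419.6 ms.
- The change in QTcB is 419.6 − 410.4 = +9.2 ms (+2.25%). QTcF is 400 ms at both rates, so its change is 0.

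**Over the range of b, 70 to 80 bpm:**

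| b | QT (ms) | QTcB (ms) | Change in QTcB | Change in QTcF |
|---|---|---|---|---|
| 0.30 | 381.9 → 366.9 | 412.5 → 423.7 | +11.2 ms (+2.71%) | +1.8 ms |
| 1/3 | 380.0 → 363.4 | 410.4 → 419.6 | +9.2 ms (+2.25%) | 0 |
| 0.40 | 376.1 → 356.5 | 406.2 → 411.7 | +5.5 ms (+1.34%) | −3.5 ms |
| 0.50 | 370.3 → 346.4 | 400.0 → 400.0 | 0 | −8.6 ms |

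A fall from 80 to 70 bpm reverses every sign.

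**Other heart-rate moves at b = 1/3.** QTcB changes by +4.7 ms (70 to 75 bpm), +8.3 ms (80 to 90), +19.6 ms (60 to 80) and −10.4 ms (70 to 60).

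**What the pair of corrections shows.** Dividing the two formulas gives QTcB/QTcF = RR^(−1/6) = (HR/60)^(1/6), whatever b is. From 70 to 80 bpm this ratio rises by a factor (80/70)^(1/6) = 1.0225. In the table the two changes accordingly differ by about 9 ms in every row (for example 11.2 − 1.8 = 9.4, and 0 − (−8.6) = 8.6). A gap between the two changes thus signals that heart rate moved and that the QTc result depends on the correction. It does not say which correction is right.

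**The case against.** The strongest reply is that little depends on QTcB and that the plan does not hide the artefact. Heart rate, RR and uncorrected QT are summarised at the same visits, the investigator's overall assessment is tabulated, and all ECG data are listed. ECG is absent from the endpoints (Protocol 6.2.1.1) and from the safety variables in Protocol 13.1.4 and SAP 2.7. No QTc threshold, outlier category or decision rule is stated. All of this stands, and it limits the weight. What it does not supply is a second set of per-subject corrected values. Separate group summaries of QT and RR do not give the mean of individually corrected QT, so a reader would have to recompute from the listing after seeing the results.

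A second reply concerns bias between treatments. A faster heart rate at an anxious first visit would be shared by both randomised sequences, and SAP 5.1.2 gives Period 2 its own baseline. Such an effect should largely cancel between SB-121 and placebo. This also stands. Within-group change from baseline has no such protection, and with at most 16 subjects chance differences in heart rate remain possible. A systematic bias between groups would need a heart-rate effect of the product, and the documents state none.

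A third reply is that footnote d of the Schedule of Events places the ECG at screening or baseline. Read as a limit, it would leave no change from baseline to distort. The schedule's ECG row also marks later visits, however, and SAP 6.7.5 plans change from baseline by visit.

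Two stronger readings are tempting. A reader might infer that QTcB is the study's only repolarisation measure; it is not, because uncorrected QT is also summarised. A reader might also infer that Fridericia should replace Bazett as the main correction. The documents do not support that ranking: at b = 0.50 QTcF itself is off by −8.6 ms while QTcB is exact.

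**Conclusion.** The point holds as a minor one. QTcB is the only heart-rate-corrected QT in the plan, and a heart-rate change can appear as, or mask, a QTc change in the descriptive tables. For a 10 bpm rise from 70 bpm the artefact runs from 0 to about 11 ms, depending on the assumed exponent. The 400 ms, the exponents and the heart rates are not document figures. The documents do not show that the artefact will occur in this trial, and they do not support a claim that the safety conclusions are biased.

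**What to change.** Add QTcF = QT/(RR in seconds)^(1/3) to the parameter list in SAP 6.7.5, with RR converted from msec to seconds (divide by 1000) before use. Calculate it for each subject and visit. Summarise it beside QTcB by treatment group, as observed values and absolute change from baseline in ms; the section already derives absolute change. Do not label either correction as the main one. State how the pair will be read: agreement between the two changes argues against a heart-rate artefact, and divergence points to one and sends the reader to the heart-rate and RR rows.

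The cost is one derived variable and one extra table row, with no new data or procedures. Specifying it before results are seen avoids a post hoc choice of correction.

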6.7.6. Physical Examination

For each physical examination body system, the number and percentage of subjects with abnormalities at baseline and at each assessed visit will be summarized by treatment group for the Safety population.

Physical examination findings (normal / abnormal) and details of abnormalities will be listed for each subject at each assessed visit for the Safety population.

6.7.7. Interim Analysis and Data Monitoring

No interim analysis and data monitoring is planned for this study.

6.8. Pharmacokinetic Assessments

No PK assessments are planned for this study.

7. Changes in the Conduct of the Study or Planned Analysis

There were no changes in the conduct of the study at the time of preparing this SAP. There were no changes in the analysis planned in the protocol of the study at the time of preparing this SAP.

